4.3 Safety Endpoints

The safety and tolerability of tozadenant will be evaluated in this study using the following measures:

- Treatment-emergent adverse events (TEAE).
- Physical and neurological examination.
- Supine and standing pulse and blood pressure.
- Standard 12-lead electrocardiogram (ECG): RR, PR, QRS, QT and QTcF.
- Laboratory parameters: hematology, chemistry, thyroid function (thyroid stimulating hormone [TSH], free T3, and free T4), and urinalysis.
- Columbia-Suicide Severity Rating Scale (C-SSRS).
- Daytime sleepiness as measured by the Epworth Sleepiness Scale (ESS), including assessment of episodes of sudden onset of sleep.
- Modified Minnesota Impulsive Disorders Interview (mMIDI).

4.4 Pharmacokinetic Variables

Tozadenant concentrations and time point of IMP intake and blood sampling

4.5 Predetermined Covariates and Prognostic Factors

The primary, secondary and exploratory analyses will be based on a mixed model repeated measures (MMRM) ANCOVA, where the covariate in the analysis is the baseline value of the respective response variable. For example, if the number of hours per day spent in the OFF state is being analyzed, the covariate will be the baseline number of hours per day spent in the OFF state. More details are provided in **Sections 9.6.1** to **9.6.3** of this SAP.

5 DEFINITIONS

5.1 Treatment Group Labels

The following treatment group labels will be used in the tables, listings and figures:

- Placebo
- 60 mg BID Tozadenant
- 120 mg BID Tozadenant
- All Tozadenant (select tables only)
- All (select tables only)

5.2 Age

The following SAS® code is used to calculate subject age (years):

Age = floor((intck('month', birth date, IC date) - (day(IC date) < day(birth date))) / 12),

where intck is a SAS® function counting integer days, date of birth is database variable BRTHDT, and informed consent (IC) date is database variable INFCDT.

5.3 Valid Diary

A valid diary will not have more than 2 hours (4 invalid entries) over a given 24-hour period. A valid diary record will not have more than 4 invalid entries (double or missed entries) over one 24-hour period. An invalid diary entry is defined as more than 1 entry recorded in a given half-hour interval, an unreadable entry, or the absence of an entry in a given half-hour interval.

5.4 Baseline for Diary Data

Baseline is defined as the average of a maximum of 3 days diary preceding the first dose.

5.5 Baseline Complete UPDRS Assessment

A valid UPDRS assessment is one in which UPDRS Part III has been completed in the ON state. The UPDRS assessment utilized as the baseline will be the later of the Screening or Baseline visit assessment that is valid.

The selected assessment will be used to determine the Baseline UPDRS Parts I-IV subscores and the UPDRS I-III total score. If a valid UPDRS is not available at Screening or Baseline visit, then the subject will be excluded from "change from baseline" UPDRS summary statistics and analyses.

5.6 Baseline for Blood Pressure and Pulse Rate

Baseline is defined as the average of the 3 pre-dose measurements for the respective supine or standing measurements that are taken following 5 minutes supine rest and following 3 minutes standing, respectively and at least 10 minutes apart prior to first dose on Day 1. Should one of the 3 measurements be missing, the baseline will be the average of the available pre-dose measurements and if two or more of the 3 measurements are missing, the baseline will be missing.

5.7 Baseline Non-Blood Pressure, Non-Pulse Rate and Non-Diary Data

Baseline is defined as the last measurement prior to first dose of study medication at study Day 1. If for any parameter the study Day 1 pre-dose value is not done or missing, then the last value obtained at a Screening visit is used as Baseline.

CONFIDENTIAL

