Part A - Footnotes:

- ^a Screening Period may not exceed 6 weeks.
- b Obtain and record BP and pulse measurements after at least 5 minutes supine rest and again after standing for approximately 1 minute and 3 minutes.
- At Screening and at Baseline (before dosing), obtain and record serial BP and pulse measurements after at least 5 minutes supine rest and again after standing for approximately 1 and 3 minutes, on 3 occasions approximately 10 minutes apart.
- ^d Optional assessments that may be performed for evaluation of AEs, at the investigator's discretion.
- Resting supine 12-lead ECGs will be collected after the patient has been in a supine position for a minimum of 5 minutes. ECGs should be collected at a time during visit when the patient is not experiencing dyskinesia that would interfere with an adequate recording. At Baseline, obtain triplicate 12-lead ECGs (3 serial readings performed several minutes apart).
- UPDRS to be measured in ON state approximately 1 to 3 hours after patients have taken a scheduled dose of levodopa (preferably their morning dose of levodopa). Patients will be instructed to have already taken their normally scheduled dose of levodopa (and their IMP for visits following randomization) before arriving at the study site in order to have their UPDRS Part III evaluated in the ON state. UPDRS in the ON state will be measured at a time representative of the ON state in that patient, not in the patient's "best" ON.
- At Screening, send patient for structured clinical interview if one or more positive mMIDI modules. If the structured clinical interview confirms that the subject does not have an ICD, he/she will not be considered ineligible on that basis. After Baseline, if patient has one or more positive modules on the mMIDI, their continued participation in the study should be discussed with the Medical Monitor.

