4.2 Exclusion Criteria

Patients with any of the following characteristics will be excluded from being randomized:

- 1. Patient previously participated in any study with tozadenant.
- 2. Patient is currently participating in or has participated in another study of an IMP or medical device in the last 3 months or within 5 half-lives of the IMP (whichever is longer).
- 3. Patient has any form of secondary or atypical parkinsonism (e.g., drug-induced, post stroke).
- 4. Severe obesity defined as a BMI greater than 35.
- 5. Patient has a QTcF interval of ≥ 500 msec at Screening (Visit 1) or the patient has an average QTcF interval ≥ 450 msec for males or ≥ 470 msec for females at Baseline (Visit 2). The average at Baseline will be taken from 3 serial ECGs done several minutes apart. (Fridericia's correction [QTcF] must be used for correction of the QT interval.)
- 6. Known diagnosis of malignant melanoma.
- 7. History of neurosurgical intervention for PD.
- 8. Patient with grade 2 hypertension (supine systolic BP ≥ 160 or diastolic BP ≥ 100 mmHg), treated or untreated, at Screening or at Baseline confirmed by at least 1 of 2 further measurements. Patients may be rescreened once if excluded due to this exclusion criterion, following appropriate treatment.
- 9. Patient with a history of hypertensive crisis unless the underlying cause has been removed.
- 10. Patient has a history of chronic alcohol or drug abuse within the last 2 years.
- 11. Patient is taking apomorphine, budipine, istradefylline, tolcapone, or within 4 weeks prior to Screening or is likely to require any of these drugs during the study.
- 12. Current treatment with antipsychotics; however, quetiapine administered at doses of ≤100 mg per day is permitted if the patient has been on a stable daily dose for at least 4 weeks before Screening. PRN (as needed) dosing is not permitted.
- 13. Exposure to neuroleptics (antipsychotic drugs) for more than 1 month within the past 2 years, or any exposure within the past year (except for quetiapine).
- 14. Patient has taken digoxin within 4 weeks prior to Screening or is likely to require digoxin during the study.
- 15. Hyperthyroidism or hypothyroidism, unless all of the following conditions are met:
 - a. Patient has received a stable dose of thyroid medication for at least 3 months before the Baseline Visit.
 - b. TSH concentrations are in the normal range (\pm 10% as a window either side of the normal range).
 - c. Patient is clinically euthyroid.

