4.3.2 Definite Criteria for Withdrawal from Study

Patients must be discontinued from the study if any of the following events occur:

- 1. Patient develops an illness that would interfere with his or her continued participation.
- 2. Patient withdraws his or her consent.
- 3. Confirmation of patient pregnancy during the study, as evidenced by a positive pregnancy test.
- 4. The Sponsor's designee or a regulatory agency requests withdrawal of the patient.
- 5. The Sponsor or a regulatory agency terminates the study.
- 6. Patient has active suicidality since last visit as indicated by a positive response ("Yes") to either Question 4 or Question 5 of the C-SSRS, or reports any suicidal behavior since their last C-SSRS assessment. The patient should be referred immediately to a Mental Healthcare Professional.
- 7. The patient has a QTcF interval consistently ≥ 500 msec and/or a QTcF interval consistently increased by ≥ 60 msec compared to the average baseline QTcF interval. The average baseline QTcF interval is defined as the average of the three QTcF interval values obtained at Visit 2. Fridericia's method must be used for correction of QT intervals.
- 8. Investigators must follow guidelines provided related to monitoring hepatic parameters in relation to investigation guidelines and stopping rules. The following necessitate immediate cessation of dosing with IMP:

- a. Patients with alanine transaminase (ALT) or aspartate transaminase (AST) >8x ULN.
- b. Patients with ALT or AST $\ge 3x$ ULN and co-existing total bilirubin $\ge 2x$ ULN*.
- c. Patients with ALT or AST $\ge 3x$ ULN who exhibit a temporally associated fatigue, nausea, vomiting, right upper quadrant pain or tenderness, fever (without clear alternative cause), rash or eosinophilia (>5%).
- *Patients with significant elevation of ALP (ALP >2x ULN) indicating biliary obstruction to be discussed with the Medical Monitor.
- 9. Patients noted to have an elevated BP post-baseline, with a systolic BP \geq 160 mmHg and/or a diastolic BP \geq 100 mmHg that is present at 2 consecutive post-baseline study visits.

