11.3 General Statistical Considerations

Descriptive statistics will be displayed to provide an overview of the study results. For categorical variables, the number and percentage of patients in each category will be presented. The denominator for percentages will be based on the number of patients appropriate for the purpose of analysis. For continuous variables, descriptive statistics will include number of patients (n), mean, standard deviation (SD), median, minimum, and maximum.

In general, Baseline values for efficacy and safety variables will be determined from the last non-missing data collected prior to the first dose of study medication.

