9.7.10 ECG

ECG data will be summarized for the following visits: Screening, Weeks 0, 2, 6, 12, 18, 24 and early termination. Descriptive statistics (n, mean, standard deviation, median, minimum and maximum) of each parameter (HR, PR, RR, QRS, QT, QTcB and QTcF) by treatment group will be displayed for the observed value and change from baseline at each scheduled listed above for the safety analysis set.

The number and percentage of subjects with maximum post-dose QT/QTcB/QTcF interval within the following ranges will be summarized by treatment group:

- ≤450 msec
- >450 msec and ≤480 msec
- >480 msec and ≤ 500 msec
- >500 msec.

In addition the number and percentage of subjects with maximum change from Baseline in QT/QTcB/QTcF interval within the following ranges will be summarized by treatment group:

- ≤30 msec
- >30 msec
- ≤60 msec, and >60 msec.

ECG findings will be classified as normal or abnormal, with abnormal values further classified according to clinical significance (yes/no). The percentage of subjects with clinically significant findings and clinically significant treatment-emergent findings will be summarized by treatment group for each visit.

All ECG data collected will be included in the data listings

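### The SAP's default ECG baseline is the last pre-dose reading, although three are recorded and the protocol uses their mean for QTcF; the change-from-baseline tables are noisier than they need be

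*SAP*

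**What the plan says.** **Data collected.** The schedule footnotes in the protocol (Table 1) and the SAP (Table 3-1) both call for triplicate ECGs at Baseline, several minutes apart. Protocol 6.2.3.3 repeats this for Visit 2.

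**Protocol, QTcF decisions.** Exclusion criterion 5 (4.2) states "The average at Baseline will be taken from 3 serial ECGs done several minutes apart". The QTcF withdrawal criterion (4.3.2) states "The average baseline QTcF interval is defined as the average of the three QTcF interval values obtained at Visit 2".

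**Protocol, analysis.** Section 11.3 gives a general rule: "In general, Baseline values for efficacy and safety variables will be determined from the last non-missing data collected prior to the first dose of study".

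**SAP.** Section 5.6 averages triplicates for blood pressure and pulse: "Baseline is defined as the average of the 3 pre-dose measurements for the respective supine or standing measurements". Section 5.7, headed as covering what is not blood pressure, pulse or diary data, says "Baseline is defined as the last measurement prior to first dose of study medication at study Day 1". It names neither ECG nor a rule for replicate readings. UPDRS has its own baseline in 5.5; ECG has none. Section 9.7.10 summarizes ECG change from baseline by visit and counts patients with "maximum change from Baseline in QT/QTcB/QTcF interval within the following ranges", with cut points at 30 and 60 msec. A separate table there counts maximum absolute post-dose intervals at 450, 480 and 500 msec.

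**The concern.** A programmer following SAP 5.7 would take one of the three Visit 2 readings, presumably the last in time, and discard the other two. The reading error in that single value then enters every post-baseline change for that patient. It matters most in the maximum-change categories. One low baseline reading raises the change at all five visits, so a patient can cross 30 msec by chance.

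The SAP would also treat two sets of triplicates from the same visit differently, averaging blood pressure and pulse but not ECG, without giving a reason. The tabulated QTcF change would be measured from a different starting point than the one the protocol uses for individual QTcF decisions. QTcF is a listed safety endpoint, so the report should be able to show these patients against one agreed baseline.

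**Working it through.** The documents give no QTcF variability, so there is no planned figure to reproduce. The size has to be shown over a range of assumptions.

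**Inputs**
- Baseline readings: 3 (protocol Table 1 footnote; 6.2.3.3).
- Post-baseline visits with one ECG each: 5 (Weeks 2, 6, 12, 18 and 24).
- Change is the later value minus baseline (SAP 5.8).
- Patients per arm: 150 (protocol 11.10).
- Assumed: within-patient SD of one ECG, s = 8 to 15 msec.
- Assumed: share of s² that varies between readings minutes apart, f = 0.25 to 1. The remainder, 1 − f, is shared by all readings at one visit and does not average out.
- Assumed: normal errors, independent visits, no drug effect.

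**Step 1: SD of change at one visit**

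Single reading: Var = s² + s² = 2s².

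Mean of three: Var = s² + s²[(1 − f) + f/3].

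| f | Var, mean of three | SD ratio, single to mean | SD larger by |
|---|---|---|---|
| 1 | 1.333 s² | √(2/1.333) = 1.225 | 22% |
| 0.75 | 1.500 s² | √(2/1.500) = 1.155 | 15% |
| 0.5 | 1.667 s² | √(2/1.667) = 1.095 | 10% |
| 0.25 | 1.833 s² | √(2/1.833) = 1.044 | 4% |

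This ratio does not depend on s.

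**Step 2: chance of a maximum change above a cut point c**

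Let b be the baseline error, with variance v = s² for a single reading or v = s²[(1 − f) + f/3] for the mean. Then

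P = ∫ [1 − Φ((c + b)/s)⁵] φ(b; 0, v) db,

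evaluated numerically. For c = 30 msec:

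| s (msec) | Single | Mean, f = 1 | Mean, f = 0.5 | Mean, f = 0.25 |
|---|---|---|---|---|
| 10 | 6.5% | 2.2% | 4.3% | 5.4% |
| 12 | 13.3% | 6.8% | 10.4% | 11.9% |

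At s = 8 the figures are 1.7% against 0.3-1.3%. At s = 15 they are 24.2% against 17.0-22.8%.

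Per arm of 150 at s = 10, this is 150 × 0.065 = 9.8 patients against 150 × 0.022 = 3.3 to 150 × 0.054 = 8.1. At s = 12 it is 150 × 0.133 = 20.0 against 10.2 to 17.9.

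For c = 60 msec the single-reading share is about 0.1% at s = 12 (0.15 patients per arm) and 1.0% at s = 15 (1.5 patients per arm). Chance alone therefore puts few patients in that row under either baseline.

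**Step 3: which tables are affected**

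The visit-wise change summaries and the maximum-change categories use baseline and are affected. The table of absolute intervals at 450, 480 and 500 msec does not use baseline and is unchanged.

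**The case against.** The strongest reply is that SAP 5.7 follows the protocol. Section 11.3 sets the last non-missing value as the analysis baseline, while 4.2 and 4.3.2 define the mean for eligibility and withdrawal, not for summary tables. This largely stands. A reader might infer that the SAP contradicts the protocol outright, but the documents do not support that. The protocol's rule is qualified as general, and the protocol holds both that rule and a specific QTcF definition without saying which governs the tables.

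Nor does 5.7 mention ECG or state that one of three readings is to be picked. The single reading is the natural default, not an explicit instruction. That limits the criticism but still leaves the baseline undefined where three readings exist.

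A reader might also infer that the QT comparison with placebo is compromised. It is not biased by this. The same rule applies in every arm, concurrent placebo is shown alongside, and 9.7.10 is descriptive with no planned test. What remains is lost precision and chance misclassification.

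Finally, it is tempting to think that a common baseline would make the SAP's row above 60 msec identify the patients who met the withdrawal criterion. It would not. The criterion requires a consistent rise of at least 60 msec, or a QTcF consistently at or above 500 msec. The SAP row counts any single maximum above 60. The two groups would differ even with the same baseline.

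**Conclusion.** The point holds as an avoidable loss of precision and an unreconciled definition. By default the SAP uses one of three recorded ECGs as baseline, although the protocol's own QTcF definitions use the mean. The affected outputs are the change summaries and maximum-change categories only.

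The direction is certain whenever readings minutes apart differ at all. The size is not, because s and f are assumptions. The 22% inflation of the SD and the fall from 6.5% to 2.2% are best cases that require fully independent readings. If only a quarter of the variance lies between readings, the inflation is 4% and the fall is from 6.5% to 5.4%. The extra chance outliers occur in all arms and make a real QTcF signal somewhat harder to see. They do not create or hide one systematically. This is a worthwhile free improvement and does not invalidate the QT safety assessment.

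**What to change.** Add to SAP 5.7 or 9.7.10: *For ECG parameters, baseline is the mean of the available pre-dose Visit 2 readings. If one of the three is missing, the mean of the other two is used; if two or more are missing, baseline is missing, as in 5.6. This is an exception to the general rule in protocol 11.3.* Section 5.7 otherwise falls back on a Screening value, so the text should say whether that fallback applies to ECG.

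Separately, reconcile the SAP's row above 60 msec with the protocol 4.3.2 criterion, or note beside the table that they count different things. This needs no change to any clinical rule.

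The cost is a few sentences in the SAP and one derivation step. The readings are already collected.

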5.8 Change from Baseline

Change from baseline will be the calculated as the later data value minus baseline.

5.9 Concomitant and Prior Medication other than Anti-PD Medications

Concomitant medications other than anti-PD medications are defined as any medications ongoing at the start of treatment or with a start date and time on or after the date of first study medication dose at study Day 1. Prior medications are defined as a medication with a stop date prior to first dose of study drug.

For the classification of medications as prior or concomitant, medications with missing or partial stop dates will be considered as follows:

- If the stop date is completely missing, the medication will be regarded as concomitant.
- If the day and month are missing but the year is given and the year is prior to the year of first dose, the medication will be classified as prior medication. Otherwise such medications will be considered as concomitant.
- If the day is missing but the month and year are given and the month and year are prior to the day of first dose, the medication will be classified as prior medication. Otherwise such medications will be considered as concomitant.

5.10 Concomitant Anti-PD Medications

During Part A, patients are required to be on a stable regimen of permitted anti-PD medications for at least 4 weeks prior to Screening (see inclusion and exclusion criteria). The stable anti-PD medication regimen must include at least four doses of a levodopa-containing medication per day, and at least one other concomitant anti-PD medication (dopamine agonists, MAO-B inhibitors, anticholinergic agents, amantadine or entacapone).

All efforts should be made to maintain patients on the same stable dose and frequency of their anti-PD medications throughout Part A. After randomization, the addition of any new anti-PD medications or an increase in the dose of any anti-PD medications is not permitted. Likewise, changes to the frequency (number of doses taken per day) or to the intervals between doses (duration of time between doses on a given day) of a patient's anti-PD medication(s) are not permitted. A PRN (as needed) dose of levodopa or other anti-PD medication would be considered a change in frequency as it is not a regular part of the daily regimen.

However, at the investigator's discretion, a decrease in the total daily dose of concomitant anti-PD medication because of medication-related AEs is permitted:

- A decrease in total daily dose should be done by lowering the number of tablets taken and must not be done by changing (lowering) the frequency (# of times per day the dose is taken).
- Following a decrease in total daily dose, the dose may be increased again but cannot exceed the dosage at randomization.

5.10.1 Baseline Total Daily Levodopa

The total daily levodopa dose at Baseline will be calculated as dose x # of tablets x frequency per day.

5.10.2 Baseline Total Daily Levodopa Equivalents

The Levodopa Equivalents (LED) of each concomitant anti-PD drug being taken at Baseline will be calculated as the total daily dose of the medication multiplied by a conversion factor to obtain the LED for the medication. The total daily LED will be the sum of each LED medication. Conversion factors for each medication will be based on **Tomlinson et al. 2010**.

5.11 Informed Consent Date

Informed consent date is the date the subject signs the informed consent and this date is recorded in the database.

5.12 Missing Adverse Event Relationship or Severity

AEs with missing relationship will be considered as having a relationship of possible to study drug. AEs with missing or unknown severity will be considered severe. A subject with missing relationship or severity for an AE will be footnoted as having missing data in the corresponding tables and listings for the AE with missing data.

